7.8.2 Laboratory data

The analyses of laboratory data will be descriptive in nature and will be based on BI standards “Handling, Display and Analysis of Laboratory Data” [6]. The following analyses will be presented for all applicable laboratory parameters:

- Descriptive statistics,
- Frequency of patients with transitions in CTCAE grade from baseline to worst and last values during treatment,
- Frequency of patients with possible clinically significant abnormalities.

CTCAE version 4.03 grades will be applied to laboratory parameters using the current BI oncology standard [6]. Possible clinically significant abnormalities are defined as CTCAE grade of 2 or greater, with an increase of at least one grade from baseline.

[figure not shown]
Baseline is defined by the last available measurement before study drug administration. In cases of repeated measurements performed for the same visit the last observation will be used for tabulations.

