At time of protocol preparation, BI 836909 has not previously been tested in humans. BCMA is not expressed on other cells than plasma cells. The anticipated side effect profile of BI 836909 based on preclinical studies comprise predominantly depletion of plasma cells and alterations of lymphatic tissues. Changes in WBC (decreases of lymphocytes and monocytes, increases of neutrophils) may occur. Lymphocytopenia may predispose to infections. Given the mode of action cytokine release syndromes may happen. Cytokine release can be associated with clinical symptoms such as fever, chills, nausea, vomiting, hypotension, dyspnoea, tachypnea, headache, tachycardia, rash, and/or hypoxia. CNS toxicities were observed with blinatumomab, the CD19xCD3 BiTE molecule. Whether this side effect is restricted to the CD19 target is still unclear. Considering the experience with other monoclonal antibodies in different indications, infusion-related reactions as well as cytokine release syndrome may occur and have to be differentiated from tumour lysis syndrome. Adverse events like these are frequently reported in patients with malignant diseases and may be due to the underlying disease, the treatment or both. Autoimmune phenomena in terms of anti-drug antibodies may occur. Prophylactic measures will be implemented in this protocol for primary prevention, supportive treatments are available (see [Sections 4.1.4.1](#) and [4.2.1.2](#)).

Current therapy for MM often cause remissions, but nearly all patients eventually relapse and die. There is substantial evidence of an immune-mediated elimination of myeloma cells in the setting of allogeneic hematopoietic stem cell transplantation. There is clearly a great need for new immunotherapies for multiple myeloma and targeting BCMA on MM cells and directing the cytolytic activity of CTLs to MM cells by a BCMA-BiTE might be a major advance in treating patient with refractory or relapsed MM.

Patients with MM may benefit from treatment with BI 836909 in terms of tumour cell reduction, tumour stabilisation, control of tumour-related symptoms and improved survival as BI 836909 targets an epitope of MM cells which has not previously been targeted. The potential benefit of therapy with BI 836909 is expected to outweigh the treatment-related risks.

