3.3.2 Inclusion criteria

1. Patients with a documented diagnosis of relapsed and/or refractory multiple myeloma who progressed after at least two prior treatment regimens, including both a proteasome inhibitor as well as an immune - modulatory drug at time of screening
2. Must have measurable disease, defined by one or more of following at time of screening:
 - a serum M protein > 0.5 g/dl measured by serum protein electrophoresis
 - urinary M protein excretion > 200 mg/24 hours
 - serum free light chain (FLC) measurement > 10 mg/dl, provided that the serum FLC ratio is abnormal
3. Relapse or progression of disease with an indication for therapy as per investigator`s judgment at time of screening
4. Life expectancy of at least 6 months as per investigator`s judgment at time of screening
5. ECOG Performance Status 0, 1 or 2 at time of screening
6. Age \geq 18 years at time of screening
7. Written informed consent which is consistent with ICH-GCP guidelines and local legislation.
8. Able to adhere to the study visit schedule e.g. ability to come to the clinic and adhere to other protocol requirements
9. Indwelling central venous catheter or willingness to undergo intra venous central line placement

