5.1.2 Assessment of Efficacy

5.1.2.1 Laboratory parameters

The following laboratory parameters must be evaluated to assess response of treatment:

- Multiple myeloma (MM) cells in bone marrow
Analysis of myeloma cells in bone marrow will be conducted using a diagnostic FACS panel including markers for CD45, CD38, CD19, CD138, CD56 and kappa/lambda chains. Scheduled sampling time points will be as follows (see [flow charts](#)): within 14 days before day 1 cycle 1 or in cycle 1, day 1 before start of treatment, when M protein/FLC becomes undetectable during treatment, on day 29 of cycle 3 and at EOT. **The analysis will be performed centrally. Percentage (%) of plasma cells in bone marrow should be assessed locally according to institutional standards and documented in eCRF at each timepoint.**
- M protein will be measured in serum at the beginning and at the end of each treatment period, i.e. at baseline (screening or Cycle 1 Day 1) and at Cycle 1 Day 29, Cycle 2 Day 1 and Cycle 2 Day 29 and Cycle X Day 1, Cycle X Day 29 and at EOT. M protein measurements in urine will only be followed up if positive for M protein in serum at

Proprietary confidential information.

© 2018 Boehringer Ingelheim International GmbH or one or more of its affiliated companies. All rights reserved.

This document may not - in full or in part - be passed on, reproduced, published or otherwise used without prior written permission.

baseline (Cycle 1 Day 1). Time points for urine analysis for M protein will be the same as for serum. **Measurements will be performed locally.**

- Free Light Chains (FLC)
In case of free kappa/lambda light chain (FLC) multiple myeloma (M protein negative cases) FLC will be analysed in serum and urine at the same time points as for M protein described above. Measurements will be performed locally. Levels of involved/uninvolved FLC, ratio of monoclonal lambda FLC / kappa FLC and ratio of monoclonal kappa FLC /lambda FLC will be determined. **Measurements will be performed locally.**
- The analysis of immunoglobulins (IgG, IgA, IgM) will be performed at baseline, followed by intervals of two weeks and at EOT. **Measurements will be performed locally.**
- β 2-microglobulin will be measured in serum as recommended for M protein described above. In urine, measurements will be done at baseline and every 6 weeks and at EOT. **Measurements will be performed locally.**

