5.2.4 Assessment of safety laboratory parameters

5.2.4.1 General safety laboratory parameters

Blood samples and urine have to be collected at the time points specified in the [flowchart](#). Safety laboratory examinations will include haematology, biochemistry, coagulation and qualitative urine analysis. **The measurements will be performed locally.**

| | |
|--------------|---|
| Haematology | Haemoglobin, red blood cell count (RBC), white blood cell count (WBC) with differential, platelets (PLT) |
| Biochemistry | Glucose, sodium, potassium, total calcium, inorganic phosphate, creatinine, aspartate amino transferase (AST), alanine amino transferase (ALT), alkaline phosphatase (AP), lactate dehydrogenase (LDH), total bilirubin (if elevated provide direct bilirubin), urea, total protein, albumin, uric acid, Ferritin (at baseline of cycle 1 only). Serum immunoglobulin levels (IgG, IgM, IgA) at baseline, day 15 and day 29 of each cycle only |
| Coagulation | Activated partial thromboplastin time (aPTT), prothrombin time (PT)/international normalised ratio (INR), fibrinogen and D-Dimers in cycle 1 and 2; thereafter on day 1 of each of the following cycles only. |
| Urine | pH, glucose, erythrocytes, leukocytes, protein, nitrite will be analysed by dipstick and reported as semiquantitative measurements. In case of pathological findings, further evaluation should be performed and results documented. |

A serum pregnancy test needs to be obtained at the time points indicated in the [flowchart](#) in patients of childbearing potential.

In case a treatment course is delayed due to an adverse event, the patient should visit the site at least once a week for assessment of safety laboratory and adverse events. More frequent visits may be appropriate as assessed by the investigator.

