7.3.4 Safety analyses

Adverse events will be coded using the Medical Dictionary for Regulatory Activities (MedDRA) coding dictionary. Standard BI summary tables and listings will be produced. Statistical analysis and reporting of adverse events will concentrate on treatment-emergent adverse events. To this end, all adverse events occurring between start of treatment and end of the residual effect period (“REP”; see definition in [Section 5.2.3](#)) will be considered ‘treatment-emergent’. Adverse events that start before first drug intake and deteriorate under treatment will also be considered as ‘treatment-emergent’.

Key measures of safety will include:

- The incidence and intensity (according to CTCAE criteria version 4.03) of adverse events;
- Time course and distribution of patients by maximum CTCAE grade according to version 4.03;
- Time course of laboratory changes

The severity and timing of adverse events will indicate the tolerability of the treatment regimen. Adverse events will be evaluated using the CTCAE grading scheme version 4.03. The overall incidence and intensity of adverse events, as well as relatedness of adverse events to treatment with BI 836909 will be reported for all dose cohorts. Serious adverse events will be tabulated. In addition, events leading to dose reduction or treatment discontinuation will be examined, but may not be reported as individual tables, depending upon the extent of overlap with the occurrence of DLT.

Laboratory data will be analysed both quantitatively as well as qualitatively. The latter will be done via comparison of laboratory data to their reference ranges. Values outside the reference range as well as values defined as clinically relevant will be highlighted in the listings.

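### The visible laboratory rule does not separate the immunoglobulin class that contains the patient's M-protein, so in that class tumour response and loss of normal antibody are mixed in the safety tables

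*SAP*

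**What the plan says.** Protocol 2.3 describes the expected toxicity: "The anticipated side effect profile of BI 836909 based on preclinical studies comprise predominantly depletion of plasma cells and alterations of lymphatic tissues". Protocol 5.2.4.1 places immunoglobulins in the general safety laboratory: "Serum immunoglobulin levels (IgG, IgM, IgA) at baseline, day 15 and day 29 of each cycle only". Protocol 5.1.2.1 lists the same three analytes among the parameters for judging response: "The analysis of immunoglobulins (IgG, IgA, IgM) will be performed at baseline, followed by intervals of two weeks and at EOT". That section also says "M protein will be measured in serum at the beginning and at the end of each treatment period", with a further value at EOT. So there is no M-protein value at day 15.

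For the analysis, SAP 7.8.2 states "The following analyses will be presented for all applicable laboratory parameters". The displays are descriptive statistics, CTCAE grade transitions from baseline, and counts of possible clinically significant abnormalities. Protocol 7.3.4 plans a quantitative and a qualitative laboratory analysis, and says of the qualitative part: "The latter will be done via comparison of laboratory data to their reference ranges". SAP 6.1 tabulates all analyses by dose group.

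No visible section separates the class that carries the M-protein from the other classes, corrects for M-protein, or tabulates by myeloma type. Heavy-chain class is not among the baseline characteristics visible in SAP 7.1.

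**The concern.** The protocol uses one measurement for two opposite purposes. As a safety value, a fall in immunoglobulin suggests that normal plasma cells are being lost. As a response value, a fall in the class that carries the M-protein suggests that the tumour is shrinking. Applied as written, the generic rule puts both in one column of the dose-group table, next to a reference range meant for normal antibody.

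At stake is how the main anticipated on-target effect is described. Under protocol 2.2, if the MTD is not reached, the recommended dose depends on safety data together with pharmacokinetic, pharmacodynamic and possibly efficacy data. A table that mixes benefit and harm is a poor basis for that description.

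**Working it through.** The plan gives no figure on this point, so there is nothing to reproduce. The check is how the measured value behaves.

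**Model.** Measured level of the involved class = M + P, where M is the M-protein and P the normal (polyclonal) antibody of that class. In uninvolved classes, and in M-protein-negative patients, M = 0.

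**Inputs from the documents**
- Entry by the serum route (protocol 3.3.2): "a serum M protein > 0.5 g/dl measured by serum protein electrophoresis". This is 5 g/L and one of three alternative ways to qualify.
- Partial response needs a serum M-protein fall of more than 50% (protocol 5.1.2.2).
- Progression needs a rise of more than 25% (protocol 5.1.2.6).
- Cohorts from 3.2 µg/day upwards have 3 to 6 patients (protocol 3.1).

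**Step 1, on the documents' own limit.** 0.5 × 0.5 g/dL = 0.25 g/dL = 2.5 g/L. The involved class falls by this much when M halves from the entry limit and P does not change. One such patient, with the others stable, moves the cohort mean change by 2.5/3 = 0.83 g/L (three patients) or 2.5/6 = 0.42 g/L (six patients).

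**Step 2, over an assumed range.** The documents do not give M above the entry limit, or P. I assume M from 5 to 40 g/L and P from 2 to 7 g/L. The formulas for the change in the measured involved class are:
- A. M falls 50%, P unchanged: −0.5M/(M + P)
- B. M unchanged, P falls 80%: −0.8P/(M + P)
- C. M rises 25%, P falls 80%: (1.25M + 0.2P)/(M + P) − 1

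| M (g/L) | P (g/L) | A: true antibody loss 0% | B: true loss 80% | C: true loss 80% |
|---|---|---|---|---|
| 5 | 2 | −36% | −23% | −5% |
| 5 | 7 | −21% | −47% | −36% |
| 20 | 2 | −45% | −7% | +15% |
| 20 | 7 | −37% | −21% | −2% |
| 40 | 2 | −48% | −4% | +20% |
| 40 | 7 | −43% | −12% | +9% |

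Over the whole range, A gives a fall of 21 to 48%, or 38 to 86% if M falls 90%. B gives a fall of 4 to 47%, and of 4 to 21% once M is at least 20 g/L. C runs from −36% to +20%.

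**Step 3, where the distortion is absent.** With M = 0, the measured change equals the change in P: 0% in A and −80% in B and C. The signal is therefore intact in the uninvolved classes and in light-chain-only disease.

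**The case against.** The strongest reply is that the defect is inferred from silence. The visible SAP body never names immunoglobulins, covers only applicable parameters, and relies on a sponsor laboratory standard that is not available here. The SAP abbreviation list defines IgA, IgG and IgM although none of them appears in the visible body, and the section numbering skips 7.6. Redacted text may well use them. This stands: the point concerns the visible rule, and a cross-reference could close it.

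A reader might infer that true antibody loss is hidden altogether. The documents do not support that. The three classes are measured separately, and protocol 7.3.4 highlights out-of-range values in listings, so low uninvolved classes can be seen patient by patient. Medians and quartiles are also planned (SAP 7), which limits the pull of one patient on a cohort summary.

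A reader might also infer that apparent antibody loss will rise with dose and distort the recommended dose. That would need response to rise with dose, which is an assumption. The safety committee also reviews all available clinical and safety data before each escalation (protocol 3.1.1), and no route to a wrong MTD or DLT count is shown.

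Finally, subtracting M-protein is a weak correction: there is no day 15 value to pair, and the difference is imprecise when M-protein is high. That stands too, and limits subtraction to a supporting role.

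**Conclusion.** The point holds in limited form. Under the visible rule, the involved class in patients with an intact serum M-protein gives a confounded safety display, and the distortion can go either way. The size that rests on the documents alone is 2.5 g/L for a 50% M-protein fall at the entry limit. The percentages rest on assumed values and illustrate direction and scale; they do not predict this trial's results. Uninvolved classes and M-protein-negative patients are not distorted, but dose-group tables of 3 to 6 patients mix them with patients who are.

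MTD and DLT counts are unaffected. The argument does not depend on whether immunoglobulins carry a CTCAE grade, since descriptive statistics and reference-range comparison are enough to create the problem. It is a worthwhile improvement to a descriptive safety display, conditional on redacted text or the sponsor standard not already providing it.

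**What to change.** Add an immunoglobulin rule to SAP 7.8.2:

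1. Classify each patient's involved heavy-chain class at baseline. Confirm that the eCRF captures it, because it is not visible in SAP 7.1.
2. Make the uninvolved classes the leading safety display (all three classes in light-chain-only disease), by dose group, with comparison against the lower reference limit.
3. Show the involved class in a separate row or table, labelled as containing M-protein.
4. Present total minus serum M-protein only as a supportive display, where both values exist: baseline, day 29 and EOT.
5. Keep the measured totals in the safety listings.

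If redacted text or the sponsor standard already does this, a cross-reference in 7.8.2 suffices.

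The cost is a few derived variables from measurements already planned, and smaller denominators per class. In a three-patient cohort whose members all share one involved class, that class has no uninvolved row, and the other two classes carry the information. No visit, dose or clinical rule changes.

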- 12 at screening and at each visit and at EOT; during hospitalization in cycle 1 safety lab should be done before start of treatment on day 1 and repeated in the evening of day 1 as well as in the morning of days 2 and 3; in cycle 2 safety lab should be done before start of treatment on day 1 and in the morning of day 2.
On day 29 of cycle 1 blood draw for safety lab should be done before the end of the infusion.
- 13 Infusion bag will have to be exchanged during continuous infusion of BI 836909 approximately every 4 days; patients should either come to the clinic or bag change will be done by a home care service.
- 14 Clinical disease assessment must be performed:
At screening, at start of each cycle as well as at EOT.
MRI must be performed:
At screening and at start of each other cycle at or within 14 days before day 1, cycle 3; day 1, cycle 5; day 1, cycle 7; day 1... and/or at time of progression based on IMWG response criteria or start of further anticancer therapy; Results from routine assessments (MRI) for multiple myeloma are accepted for screening if performed within 28 days before start of treatment.
Clinical disease status will be assessed at screening and at the start of each new cycle (e.g. before cycle 2, 3, 4 and 5 etc.) as well as at EOT.
- 15 see separate [Flow chart](#); [Appendix 10.2](#).
- 16 Orienting neurological examination should be performed at screening as well as at EOT and daily during hospitalization required by the protocol.

Proprietary confidential information.

© 2018 Boehringer Ingelheim International GmbH or one or more of its affiliated companies. All rights reserved.

This document may not - in full or in part - be passed on, reproduced, published or otherwise used without prior written permission.

Proprietary confidential information.

© 2018 Boehringer Ingelheim International GmbH or one or more of its affiliated companies. All rights reserved.

This document may not - in full or in part - be passed on, reproduced, published or otherwise used without prior written permission.

TABLE OF CONTENTS

[figure not shown]
[figure not shown]
| | |
|--|----------|
| TITLE PAGE | 1 |
| CLINICAL TRIAL PROTOCOL SYNOPSIS | 2 |
| FLOW CHART: BI 836909 CONTINUOUS INTRAVENOUS INFUSION | 7 |

| | |
|--|-----------|
| TABLE OF CONTENTS | 11 |
| ABBREVIATIONS | 16 |
| 1. INTRODUCTION..... | 20 |
| 1.1 MEDICAL BACKGROUND..... | 20 |
| 1.2 DRUG PROFILE | 21 |
| 2. RATIONALE, OBJECTIVES, AND BENEFIT - RISK ASSESSMENT | 24 |

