5.2.4.2 Screening for laboratory evidence of tumour lysis syndrome

Tumour lysis syndrome (TLS) is characterized by metabolic derangements caused by the massive and abrupt release of cellular components into the blood after rapid lysis of malignant cells. The release of the intracellular metabolites can overwhelm normal homeostatic mechanisms, potentially leading to hyperuricemia, hyperkalemia, hyperphosphatemia, hypocalcemia, and uremia. This can result in impaired renal function, and in some cases, in acute renal failure and even death ([R10-4517](#)). To allow for early treatment in case TLS develops, vigilant monitoring is recommended if clinically indicated. During the first 48 hours after the start of the first infusion/injection of BI 836909 in course 1, and during the first 24

Proprietary confidential information.

© 2018 Boehringer Ingelheim International GmbH or one or more of its affiliated companies. All rights reserved.

This document may not - in full or in part - be passed on, reproduced, published or otherwise used without prior written permission.

hours after the start of the first infusion/injection in course 2, the below listed laboratory parameters need to be determined to screen for evidence of a tumour lysis syndrome monitored frequently, i.e. every 4-8 hours between the time points at which a complete safety laboratory has to be performed. The actual date and time of the blood samples should be recorded in the eCRF.

| | |
|--------------|--|
| Haematology | haemoglobin, haematocrit, red blood cell count (RBC), white blood cell count (WBC),+ differential, platelets (PLT) |
| Biochemistry | uric acid, potassium, calcium, inorganic phosphate, lactate dehydrogenase (LDH), creatinine, urea, ferritin. |
| Coagulation | Activated partial thromboplastin time (aPTT), prothrombin time (PT)/international normalised ratio (INR), fibrinogen, D-dimer. |

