6.2.4 Treatment period(s)

The first study drug dose should occur at the latest at Day 21 after the first screening procedure has been performed. A treatment cycle is defined as 6 weeks of duration. If initiation of a subsequent cycle is delayed due to medical reasons, additional visits beyond Day 36 may be necessary and may be performed at investigator's discretion, and should be recorded in the eCRF.

Patients may continue treatment in case of clinical benefit for 5 cycles. In case of ongoing clinical benefit up to a maximum of 5 additional treatment cycles can be given if considered indicated by the treating investigator.

6.2.4.1 Cycle 1

Patients will be hospitalized for the first 3 – 4 days.

Table 6.2.4.1: 1 Visit 1 (Day 1-3 or 4)

| | |
|---|--|
| Physical examination (Section 5.2.6.2) | A general physical examination will be performed, preferably by the same investigator through the study to enable comparability. This includes blood pressure, heart rate and temperature. Additional time points for blood pressure, heart rate and body temperature at the day of start of administration of BI 836909 are: prior to the start of premedication and infusion, then every 30 (± 10) minutes after start of the infusion of BI 836909 for the first 4 hours and additionally 3 times during hospitalisation (in the evening of day 1 as well as in the morning of day 2 and 3). Orienting neurological examination daily during hospitalisation. |
| Weight (Section 5.2.6.2) | Weight is measured; preferably, the same weight scale should be used throughout the study to ensure consistency of data collected. |
| PK samples (Section 5.5 and 5.2.5) | For PK sampling, see separate Flow chart as well as section 5.5 |
| Safety laboratory (Section 5.2.4) | Haematology, biochemistry, coagulation parameters and urinalysis (dipstick). |
| Adverse events (Section 5.2.2) | Occurrence of AEs since last visit. |
| Concomitant therapies (Section 4.2) | Any new or any change in concomitant therapies since the last visit, will be recorded in the eCRF. |

Proprietary confidential information.

© 2018 Boehringer Ingelheim International GmbH or one or more of its affiliated companies. All rights reserved.

This document may not - in full or in part - be passed on, reproduced, published or otherwise used without prior written permission.

Table 6.2.4.1: 1 (cont'd) Visit 1 (Day 1-3 or 4)

| | |
|---|---|

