6. GENERAL ANALYSIS DEFINITIONS

6.1 TREATMENTS

Patients are administered BI 836909 as a continuous 4-week infusion followed by a 2-week break for 5 cycles or until progression, unacceptable adverse events or other reason necessitating withdrawal. In case of ongoing clinical benefit a maximum of 5 additional treatment cycles can be given.

[figure not shown]

Figure 6.1:1 Overall study design

For all analyses, statistics will be tabulated by treatment dose group (see [Table 6.1: 1](#)).

Table 6.1: 1 Treatment labels for use in the CTR

Treatment label	Short label
BI 836909, 0.2 µg/d, c.i.v. ^[1]	0.2 µg/d civ
BI 836909, 0.4 µg/d, c.i.v. ^[1]	0.4 µg/d civ
BI 836909, 0.8 µg/d, c.i.v. ^[1]	0.8 µg/d civ
BI 836909, 1.6 µg/d, c.i.v. ^[1]	1.6 µg/d civ
BI 836909, 3.2 µg/d, c.i.v.	3.2 µg/d civ
BI 836909, 6.5 µg/d, c.i.v.	6.5 µg/d civ
BI 836909, 13 µg/d, c.i.v.	13 µg/d civ
BI 836909, 25 µg/d, c.i.v.	25 µg/d civ
BI 836909, 50 µg/d, c.i.v.	50 µg/d civ
BI 836909, 100 µg/d, c.i.v.	100 µg/d civ
BI 836909, 200 µg/d, c.i.v.	200 µg/d civ
BI 836909, 400 µg/d, c.i.v.	400 µg/d civ
BI 836909, 800 µg/d, c.i.v. ^[2]	800 µg/d civ

[1] The 1st four treatment label (0.2 – 1.6 µg/d) may be combined into one column for selected displays.

[2] Further doses will be tested in case that MTD could not be confirmed at a dose level of 800 µg/day. Intermediate doses cohorts will be entered if determined by the safety committee, for example, in case that the dose cohort 400 µg/day exceeds MTD (>1 patients out of 6 with DLT) and no DLT is observed on 200 µg/day, 300 µg/day might be considered.

The purpose of the definition below is to describe the different study interval in this trial.

The treatment periods of the study are:

- Screening period:
The screening period starts from the date of informed consent and ends at the date of the first administration of study drug.
- Treatment period:

Treatment period starts from the date of the first administration of study drug and ends at the date of the last administration of study drug.

- Residual effect period:

Residual effect period starts from the date of the last administration of study drug + 1, and ends at the date of the last administration of study drug + 30 days .

- Follow-up period;

The Follow-up period starts from the last administration of study drug + 30 days.

Please see [Table 6.1:2](#) below, for a definition of treatment periods. The purpose of the definitions below is to describe the treatment periods in this trial.

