6.7 BASELINE, TIME WINDOWS AND CALCULATED VISITS

In general, baseline values will be the measurements taken most recently prior to the first administration of study drug. If this value is not available, the measurement at screening visit will be used. If the lab is repeated at screening, then the last one should be used.

For efficacy analyses, baseline is defined as the pre-treatment observation at C1V1. If C1V1 is missing, then Screening will be used for baseline.

Visit will be labelled according to the flow chart in the protocol: Study day will be calculated relative to the date of the first administration of study drug. The day prior to first administration of study drug will be 'Day -1' and the day of first administration of study drug will be 'Day 1'; therefore 'Day 0' will not be used.

Clinical disease status will be assessed at screening and at the start of each new cycle (e.g., before Cycle 2, 3, 4 and 5, etc.) as well as EOT.

While nominal times listed in this section should be adhered to as closely as possible, the actual sampling times will be recorded and used for determination of pharmacokinetic parameters.

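### SAP 7.8.2 does not exempt the worst-grade laboratory tables from its last-value-per-visit rule or define their window, so early peaks and post-stop values can be lost from them

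*SAP*

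**What the plan says.** SAP 7.8.2 plans three laboratory outputs: descriptive statistics, a shift table described as "Frequency of patients with transitions in CTCAE grade from baseline to worst and last values during treatment", and the frequency of possible clinically significant abnormalities (CTCAE grade 2 or more with a rise of at least one grade from baseline). The section closes with the selection rule "In cases of repeated measurements performed for the same visit the last observation will be used for tabulations". Other detail is left to an internal sponsor standard on laboratory data (SAP reference 6).

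On visits, SAP 6.7 states: "Visit will be labelled according to the flow chart in the protocol". The protocol flow chart and Table 6.2.4.1: 1 treat days 1 to 3 or 4 of cycle 1 as one visit, Visit 1. Flow chart footnote 12 requires a safety laboratory before treatment on day 1, "repeated in the evening of day 1 as well as in the morning of days 2 and 3". Protocol 5.2.4.2 adds tumour-lysis draws over the first 48 hours of course 1, "every 4-8 hours between the time points at which a complete safety laboratory has to be performed".

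On the window, SAP 6.1 states: "Treatment period starts from the date of the first administration of study drug and ends at the date of the last administration". The same section assigns adverse events to Treatment up to 30 days after the last administration. It says nothing equivalent for laboratory values.

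**The concern.** The protocol samples densely at the start of the first infusion because acute change is expected then. Protocol 2.3 anticipates transaminase rises with infusion reactions or cytokine release, and shifts in white cell counts. A rule that keeps the last value of a multi-day visit favours the recovered value over the peak.

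The window raises a similar problem at the other end of treatment. If a patient stops permanently for toxicity and a laboratory value then worsens, the matching adverse event is counted as on treatment, but the value may not be.

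These tables are the planned by-dose summary of laboratory toxicity that does not pass through investigator judgement. Laboratory changes become events only if the investigator judges them clinically relevant (Protocol 5.2.3). Grade 3 or higher laboratory findings are not DLTs if judged not clinically relevant or if they respond to routine management (Protocol 5.2.1.1). Listings show single values but give no rates by dose.

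**Working it through.** The plan states no figure to reproduce. The check counts scheduled draws and applies the SAP sentences literally.

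**Inputs**
- Cycle 1 Visit 1 full panels (footnote 12): pre-dose day 1, evening day 1, morning day 2, morning day 3.
- Later cycle 1 visits, one full panel each (flow chart): Visits 2 to 6, on days 8, 15, 22, 29 and 36.
- Tumour-lysis draws (Protocol 5.2.4.2): every 4 to 8 hours, for 48 hours in course 1 and 24 hours in course 2. Their analyte list includes neither ALT nor AST.
- EOT visit (Protocol 3.1 and 6.2.5.1): no later than 1 week after discontinuation, with a safety laboratory. The later REP visit lists none.

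**Last value per visit**
- Visit 1: 1 pre-dose + 3 post-dose = 4 full panels. One post-dose panel is kept, so 3 − 1 = 2 are dropped (evening day 1 and morning day 2).
- All of cycle 1: 3 + 5 = 8 post-dose full panels; 1 + 5 = 6 are kept and 2 dropped.
- Tumour-lysis analytes, course 1: 48/8 = 6 to 48/4 = 12 draw slots. Full panels fill some of these slots, so the two counts must not be added. If all slots carry the Visit 1 label, one is kept and 5 to 11 are dropped.
- Cycle 2 Visit 1: the only post-dose full panel (morning day 2) is kept. The 24/8 = 3 to 24/4 = 6 tumour-lysis slots could lose draws.

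**Illustration (hypothetical patient).** ALT is grade 4 on the morning of day 2, grade 1 on the morning of day 3, and no higher than grade 1 afterwards. Using all values, the worst grade is 4 and the patient counts as having a possible clinically significant abnormality. With the last value per visit taken first, the worst grade is 1 and the patient does not count, because the threshold is grade 2. If a later visit again showed grade 4, the shift table would still show grade 4.

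**Share of Visit 1 peaks at risk.** The documents do not say when peaks occur. If a peak were equally likely at each of the three post-dose panels, 2/3 would fall on a dropped panel. The share is 0 if every peak is at the last draw and 1 if every peak is earlier. Even then, a grade is lost only if it has fallen by the last draw and is not reached again at a later visit.

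**Window**
- SAP 6.1 Treatment period: ends at last dose + 0 days.
- Adverse-event window: ends at last dose + 30 days.
- EOT panel taken d days after the last dose, with d from 1 to 7: d > 0, so outside the Treatment period; d ≤ 30, so inside the adverse-event window. One scheduled panel per patient is exposed, plus any unscheduled ones.

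**The case against.** **The SAP asks for the worst value.** It names worst and last as separate quantities and does not say that worst is taken after the last-value selection. It also uses the pre-dose Visit 1 sample as baseline, so it does tell samples within that visit apart. At screening (SAP 6.7) it uses the word repeated for a re-test, not a scheduled series. This stands as an argument that the loss may not be intended. It does not settle the text: footnote 12 calls the day 1 to 3 draws repeated, and 7.8.2 does not give the order of the two steps.

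**The internal standard may resolve it.** SAP reference 6 could define both the worst-value derivation and the laboratory window. That stands, and it is why the loss cannot be called certain.

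**The window is inferred.** Section 7.8.2 does not itself cut off at the last dose; the cut-off comes from 6.1. Values taken during a temporary interruption that ends in a restart lie between first and last dose and stay in. Only values after permanent discontinuation are exposed.

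**Other outputs catch the important events.** SAP 7.8.1 plans tables for DLTs, grade 3 or higher events and events of special interest. The last group includes cytokine release, tumour lysis and hepatic injury, and hepatic injury is itself defined by laboratory thresholds. Protocol 7.3.4 highlights out-of-range values in listings. This stands and limits the consequence.

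A reader might infer that the SAP removes all day 1 to 3 peaks, that grade 3 to 4 laboratory toxicity will therefore be understated, and that the recommended dose will be distorted. The documents do not support this. The last Visit 1 draw is kept, the order of derivation is unstated, and no section ties the 7.8.2 tables to the dose decision. Protocol 3.1.1 has the safety committee review all available clinical and safety data. Protocol 5.2.1 bases the MTD on cycle 1 DLTs.

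**Conclusion.** The point holds in a limited form. As written, the last-value rule has no exemption for the two tables that depend on extremes. Read literally, it drops 2 of the 3 post-dose full panels of cycle 1 Visit 1 (2 of 8 across cycle 1). The only general Treatment period in the SAP leaves out an EOT panel taken 1 to 7 days after the last dose. Either gap can understate laboratory toxicity in the shift and possible-clinically-significant tables.

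This rests on three assumptions: flow-chart visit labels are used, the scheduled day 1 to 3 draws count as repeated measurements, and the internal standard does not override the SAP text. The number of patients affected cannot be derived from the documents. The DLT count and the MTD are not affected, and clinically relevant changes remain visible in the adverse-event tables and listings. It still deserves correction, because it concerns a stated rule and a stated period, not just missing detail.

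**What to change.** Amend SAP 7.8.2 as follows:

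1. Derive worst-grade shifts and possible clinically significant abnormalities from all values after the first dose: scheduled, repeated and unscheduled.
2. Restrict the last-observation rule to by-visit descriptive statistics, and show cycle 1 Visit 1 by planned day and time.
3. Define the laboratory on-treatment window as first dose to last dose + 30 days, matching the adverse-event window.

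If the internal standard already does this, one sentence in 7.8.2 saying so is enough.

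The cost is SAP wording, a derivation flag and slightly more programming; no new data are needed. One downside is that some values after the stop may reflect the disease or subsequent therapy. Protocol 6.2.5.2 already records anti-cancer therapy given between EOT and the REP visit, so values after its start can be flagged.
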